## 6.0 Data entry, collection, and quality control

*Data collection and management for the proposed project will be performed via a custom web-based electronic data capture system (EDC), implementing each of the CRFs described above in electronic format (eCRFs), and built using the Ruby on Rails (RoR) platform.*

This system is currently in place and actively functioning as the digital infrastructure for BetrNET, the NIH funded nationwide Barrett's disease monitoring network. The established HIPAA compliant technology has been actively in use for more than 5 years, as has a demonstrated track record of data privacy and fidelity. The system is based on *the Ruby on Rails (RoR) platform*. RoR is an open-source web application development framework for creating rich Internet applications that model complex data and reinforce data integrity through custom validations. The RoR framework for web-based data entry will be linked to a MySQL database for the data storage component. All data entry interfaces will utilize dropdown menus, radio buttons/checkboxes, and other structured variable formats whenever feasible, to enforce consistency of variable values in data entry. Also to support data quality control, extensive validations will be developed; these validations check records for internal consistency, conformity to any pre-specified data ranges, as well as compliance with any known inter-variable relationships. Support for longitudinal data will be provided through the use of a relational database architecture that models one-to-many relationships.

*In addition to the use of structured variables and validations to prevent data entry errors, other mechanisms for data quality control include:*

- Testing. The EDC will be tested extensively in both the development/staging and production environments. Automated testing is performed via scripted tests, to verify that observed

behavior of the system conforms to expected behavior. Manual testing of all system features will also be employed via the user interface and performed by dedicated testing personnel.

- Access controls. Access to the EDC will be restricted to authorized personnel. Data entry personnel and other users are provided secure access to the web-based application via standard Internet technologies (i.e., HTTPS), with tiered access permissions appropriate to their study role; such access is granted only when the following criteria are met: 1) request for access is authorized by a study principal investigator or other designated key study personnel and is accompanied by a designation of the user's role, to ensure appropriate level of access; and 2) the user completes training on system use, which may include a live training provided by our group and/or documented completion of a pre-recorded video training.

### **Patient Surveys:**

A critical component to understanding the patient experience with their disease is their own subjective input. This will be accomplished with established surveys of metrics for patient related health outcomes. The Vanderbilt University Office of Research will be used as a central location for data processing and management for these surveys. Vanderbilt University, with collaboration from a [consortium](#) of institutional partners, has developed a software toolset and workflow methodology for electronic collection and management of research and clinical trial data. Two of those technologies are REDCap (Research Electronic Data Capture), a secure, web-based application that is flexible enough to be used for a variety of types of research and the BetrNet Ruby on Rails (ROR) platform. Both provide an intuitive user interface that streamlines project development and improves data entry through real-time validation rules (with automated data type and range checks). They also provide easy data manipulation (with audit trails for reporting, monitoring and querying patient records) and an automated export mechanism to common statistical packages (SPSS, SAS, Stata, R/S-Plus). In addition to traditional data capture functionality; REDCap and ROR survey capabilities are a powerful tool for building and managing online surveys. The research team can create and design surveys in a web browser and engage potential respondents using a variety of notification methods. All data collection projects rely on a thorough, study-specific data dictionary, defined by all members of the research team in an iterative, self-documenting process. This iterative development and testing process results in a well-planned and individualized data collection strategy. Surveys will either be completed via REDCap, the Ruby on Rails (RoR) platform or a combination.

### **Patient Generated Health Data:**

One important element of research is an understanding of the experiences of individual patients, and one of the ways to learn about those experiences is by collecting patient-generated data. Such information can be obtained in a variety of ways, including during medical visits, through use of smartphones and other electronic devices, and as part of research studies. These techniques will be employed during our study to capture patient self-reported peak-flow measurements. An established REDCap-based platform will be used to allow patients to input their data and provide the ability to track these measurements longitudinally over time. This technology utilizes smartphone reminders and automated voice algorithms for patient phone call, as well as having options for secure encrypted HTTPS data transfer over the web to the servers in the Data monitoring center.

The survey REDCap servers are housed in a local data center at Vanderbilt, and all web-based information transmission is encrypted. REDCap was developed specifically around HIPAA-Security guidelines and is recommended to Vanderbilt researchers by both our Privacy Office and Institutional Review Board. REDCap has been disseminated for local use at more than 940 other academic/non-profit consortium partners in 75 countries. Vanderbilt leads the REDCap Consortium, which currently supports more than 99,000 projects and 128,000 users. More information about the consortium and system security can be found at <http://www.projectredcap.org/>.

## **7.0 Patient Reimbursement:**

None

## **8.0 Risks**

Minimal risk is anticipated. There are no investigational treatments under study in this project. Study patients will be asked to answer questions on self-administered hard copy electronic, mailed, or telephone surveys, and self-reported health data (i.e. peak flow breathing measurements).

Additionally, limited information from their routine medical care will be obtained. Patients will be informed that they can refuse to answer any of the questions. They will also be told that refusal to participate in the study will not in any way change or alter the care they will receive. Patients will be told that survey data are to be obtained for research purposes only and that no individual results will be reported. The data will be kept strictly confidential. No data of any sort will be released to anyone outside the study for any reason. Individual patients are never identified in publications.

Risks to the participants will be minimized by proper screening of potential candidates and strict adherence to confidentiality rules. In addition, access to the Electronic Data Capture (EDC) system will be strictly restricted to authorized personnel. Data entry personnel and other users are provided secure access to the web-based application via standard Internet technologies (i.e., HTTPS), with tiered access permissions appropriate to their study role; such access is granted only when the following criteria are met: 1) request for access is authorized by a study principal investigator or other designated key study personnel and is accompanied by a designation of the user's role, to ensure appropriate level of access; and 2) the user completes training on system use, which may include a live training provided by our group and/or documented completion of a pre-recorded video training. 3) The user has appropriate training for protection of human subjects.

All requests for user access, with documentation of fulfillment of the above criteria, are recorded in the permanent system documentation.

## **9.0 Benefits**

The risks for this study are minimal given the potential benefits to patients and society of any insights gained regarding the comparative effectiveness of idiopathic subglottic stenosis. Patients will be offered remuneration for study participation, as the various surveys will include roughly 25-100 items. There are no other direct benefits to the study patients, although some patients may gain

personal satisfaction through participation in research aimed at advancing knowledge of optimal treatment in a rare disease requiring repeated invasive operative interventions.

#### **10.0 Reporting of Adverse Events Involving Risk to Participants or Others**

This is a non-intervention study and there is no DSMB. The Principal Investigator is responsible for monitoring protocol conduct and reporting any adverse events related to study procedures. Adverse Events (AE) reporting will include the reporting of any unanticipated AE if it is probably or definitely related to being in this study. Although AEs are not anticipated on this study, if they should occur, they will be reported to the participating sites IRB board as well as the Vanderbilt Institutional Review Board by the Principal Investigator as required.

#### **11.0 Study Withdrawal/Discontinuation**

Study participants may withdraw from the study at any time by contacting the site specific PI, or the Coordinating Center PI [name], or coordinating center research team staff.

Subjects are free to withdraw from participation in the study at any time upon request.

An investigator may terminate a study subject's participation in the study if:

- Any medical condition, event or situation occurs such that continued participation in the study would not be in the best interest of the subject.
- The subject meets an exclusion criterion (either newly developed or not previously recognized) that precludes further study participation.

#### **12.0 Statistical Considerations**

##### **Study Hypotheses**

1. There is variation in Time to Recurrence (TTR) between centers using similar surgical approaches for iSGS
2. There is variation in TTR between centers using different surgical approaches for iSGS.
3. The different surgical approaches are associated with unique tradeoffs in terms of voice, swallowing, breathing, and global quality of life.

##### **Sample Size Considerations**

The primary endpoint of this trial is time to recurrence. The sample size estimation is completed using the 95% confidence interval (CI) method. With the proposed sample size of 1100 (endoscopic therapy  $\approx$  800, open surgery  $\approx$  100 and endoscopic resection  $\approx$  100), the half-width of

the 95% confidence interval for the time to recurrence function will be less than .24 for endoscopic resection and open surgery groups, and will be less than .13 for the endoscopic dilation group.

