## **STATEMENT OF COMPLIANCE**

The study will be conducted in accordance with the International Conference on Harmonisation guidelines for Good Clinical Practice (ICH E6), the Code of Federal Regulations on the Protection of Human Subjects (45 CFR Part 46), and the PCORI Clinical Terms of Award. All personnel involved in the conduct of this study have completed human subjects protection training.

[figure not shown]
Title:	Treatment Alternatives in Adult Rare Disease; Assessment of Options in Idiopathic Subglottic Stenosis
Précis:	The proposed study intends to create an international, multi-institutional prospective cohort of iSGS patients. It will enable rigorous treatment strategy comparisons to determine how well the most commonly used treatments in iSGS “work”; and what quality of life trade-offs are associated with each approach.
Objectives:	
Prospective rigorous treatment comparisons to provide the critical information to patients to allow them to answer the questions,
 

1) “given my personal characteristics, conditions and preferences, what should I expect will happen to me?” and

2) “what are my options and what are the potential benefits and harms of these options?”

 
Primary Endpoint: Treatment effectiveness: time to recurrent procedure and need for tracheostomy.
 
Secondary Endpoint: Health and quality of life tradeoffs: patient reported outcome measures in voice, swallowing, breathing, and global quality of life

Population:	All clinically confirmed iSGS patients at the participating institutions are eligible for enrolment.
Number of Sites:	45 Sites
Study Duration:	60 months
Subject Participation Duration:	>6months
Estimated Time to Complete Enrollment:	24 months

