## 5.0 Study Procedures

**Recruitment and Enrollment:** We anticipate a sample size of 800-1100 patients recruited across the participating centers. The target goal for Vanderbilt recruitment is 750-800 patients. There are currently 40 confirmed participating sites that will contribute patients (additional centers may be added in protocol amendments provided they meet defined study site selection criteria). Participating centers include those across all regions of the U.S. and international sites in the UK. Many are academic centers that are tertiary referral centers for adult laryngotracheal stenosis (LTS) and thus have significant experience treating this rare condition. Nearly all LTS patients are ultimately referred for care and cluster at such high-volume centers, and thus we anticipate enrolling a representative patient cohort. Each research site has appropriate technological infrastructure for data collection and pathologic specimen tracking.

Study participants will be recruited via several mechanisms. Direct recruitment by participating clinician providers that diagnose and treat these patients will occur at each of the participating centers. It is expected that the majority of patients will be recruited through this approach. Patients will be identified by PI, Sub-I or Key study personnel and approached by a member of the research team at each institution regarding the study, or contacted by phone or email about the study. Participants may also be seen due to referrals in to participating sites/providers.

Additionally interested stakeholders can identify this study directly through its registration with ClinicalTrials.gov, the National Organization for Rare Disorders (NORD) website and rare disease database. Once recruited patients will undergo detailed discussion regarding risks and benefits of the trial, and informed consent will be obtained.

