### **Final Analysis Plan**

**The primary objective:** The primary objective of this study is to evaluate the time to recurrence (TTR) among three possible treatment groups, i.e., open surgery, endoscopic dilation, and endoscopic resection.

**Data analysis plan for the primary endpoint:** Demographic information will be tabulated. Descriptive statistics, including means, standard deviations, and ranges for continuous parameters, as well as percents and frequencies for categorical parameters, will be presented. For the primary objective analysis, i.e., estimating the TTR with 95% confidence interval, the TTR time will be estimated using the Kaplan-Meier method with the 95% confidence interval (CI). The Rothman CI, CI's based on Greenwoods variance, Thomas and Grunkemeier CI and the simultaneous confidence bands by Nair and Hall and Wellner will be reported. The logrank test will be used to compare the equality of survival curves. The generalized Wilcoxon and log-likelihood tests will also be examined, as these tests weight the survival function differently from the logrank test, which gives more weight to later occurring events. The Cox proportional hazards model will be applied to investigate potential prognostic factors, such as age on the TTR data. The adjusted p-values as well as the adjusted 95% confidence intervals from the Cox model will be reported. The adjusted hazard ratios and 95% CIs will be reported.

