## **16.0 Publication/Data Sharing Policy.**

This study will comply with Public Access Policy from both PCORI and the NIH, which ensures that the public has access to the published results of NIH funded research. It requires scientists to submit final peer-reviewed journal manuscripts that arise from NIH funds to the digital archive [PubMed Central](https://pubmed.ncbi.nlm.nih.gov/) upon acceptance for publication.

Like PCORI, the NoAAC study team is committed to promoting the principles of transparency, replication and reproducibility in research. As soon as we received notification of funding, we would update the protocol for the three-year follow-up. We would not finalize it, however, until after the initial meetings of the full study team to ensure we captured patient partner opinions and generated a protocol that reflected what we truly intended to do. This would be submitted to PCORI and made available to other researchers, after approval from the PI (and the rest of the NoAAC Steering Committee study team). Additional study documentation (e.g., database design, programming code, and data definitions) would be shared with PCORI in the final year of the grant, as well as with requesting researchers, and any requesting peer-reviewed journals.

We will share all a complete, cleaned, de-identified copy of the final data set with PCORI in the third year of the grant. Additionally, we will share all code books, meta-data related to the datasets and statistical programming code with PCORI in the third year of the grant and with any peer-reviewed journals who requested this information in support of manuscripts that resulted from the project. We plan this approach with the upcoming submission of the NoAAC RP-01 results, are prepared to do this again in the future.

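### The sample size of 1100 is broken down into groups that sum to 1000, and the stated half-width bounds, though met, cannot be reproduced

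*Combined protocol and SAP*

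**What the plan says.** Protocol section 12.0, Sample Size Considerations, sizes the study by confidence-interval precision for time to recurrence. It begins "With the proposed sample size of 1100 (endoscopic therapy" and continues with about 800 for that group, about 100 for open surgery and about 100 for endoscopic resection. It then bounds the half-widths. For the two smaller groups it says: "the 95% confidence interval for the time to recurrence function will be less than .24 for endoscopic resection and open surgery groups". For the largest group the sentence ends with a second bound: "and will be less than .13 for the endoscopic dilation group". The group of about 800 is called endoscopic therapy in the breakdown and endoscopic dilation in the bound; I take these to be the same group.

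Three other places bear on this:

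- Section 5.0, Recruitment and Enrollment: "We anticipate a sample size of 800-1100 patients recruited across the participating centers".
- Section 12.0, Final Analysis Plan: the primary objective covers "three possible treatment groups, i.e., open surgery, endoscopic dilation, and endoscopic resection". The planned intervals for the Kaplan-Meier estimate are "The Rothman CI, CI's based on Greenwoods variance, Thomas and Grunkemeier CI", plus the simultaneous bands of Nair and of Hall and Wellner.
- The summary table after the Statement of Compliance: a study duration of 60 months, "Estimated Time to Complete Enrollment" of 24 months, and subject participation of more than 6 months. Section 16.0 also says "we would update the protocol for the three-year follow-up".

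**The concern.** This is the only justification given for the sample size. It rests on precision alone, with no power or effect size behind it. If the total and its parts disagree, a reader cannot tell how many patients each group is meant to have. The 100 patients left over are as many as a whole comparator group.

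The two half-width bounds ought to let a reader check the design, but they look far too wide for the sizes printed beside them. Without the assumptions behind them, nobody can tell whether they allow for heavy censoring, a late time point, a simultaneous band or something else. The precision actually planned for the primary endpoint is therefore unknown.

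**Working it through.** **Total against groups.** 800 + 100 + 100 = 1000, and 1100 − 1000 = 100, which is 100/1100 = 9.1% of the stated total. The analysis plan lists three groups and no other.

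**Attempt to reproduce .24 and .13.** The inputs are n = 100 and n = 800 from the sample-size statement, and a two-sided 95% level (z = 1.96). The statement gives no survival probability, so I take the worst case.

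*Pointwise, no censoring.* Half-width = 1.96 × √(.25/n).

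- n = 100: 1.96 × .05 = .098
- n = 800: 1.96 × .01768 = .035

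Both are below the stated bounds. Solving the same formula for n, n = .25 × (1.96/h)², gives about 17 patients for h = .24 and about 57 for h = .13.

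*Pointwise, with censoring.* The large-sample Greenwood half-width is 1.96 × S(t) × √(s²(t)/n), where s²(t) is the integral from 0 to t of λ/[S(u)G(u)] du. S is exponential with rate λ, G(u) is the probability of still being under follow-up at u, and the result is maximised over S(t) from .05 to .95. The documents give no censoring pattern for this calculation, so both patterns below are assumptions:

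- Follow-up uniform over 36 to 60 months. The minimum is 60 − 24 = 36 months if everyone is followed to study end; section 16.0 also refers to three years.
- Follow-up uniform over 6 to 60 months, a harsher pattern that takes the participation entry of more than 6 months as the minimum.

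*Simultaneous band, no censoring.* The Hall-Wellner half-width is 1.358/√n (large-sample critical value).

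| Interval and assumption | n = 100 | n = 800 |
|---|---|---|
| Stated bound | < .24 | < .13 |
| Pointwise, uncensored | .098 | .035 |
| Pointwise, month 36, follow-up 36–60 months | .098 | .035 |
| Pointwise, month 36, follow-up 6–60 months | .118 | .042 |
| Pointwise, month 48, follow-up 36–60 months | .104 | .037 |
| Pointwise, month 48, follow-up 6–60 months | .138 | .049 |
| Hall-Wellner band, uncensored | .136 | .048 |

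Other uncensored variants do not produce the pair either. For n = 100 and 800, Wilson (Rothman-type) intervals give .096/.035, exact binomial intervals .102/.035, and three-group Bonferroni intervals .120/.042. A Nair-type band with an assumed critical value of 3 gives .150/.053.

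**Where the other 100 might go.** Uncensored pointwise half-widths for each possibility:

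- All to dilation (n = 900): .033 instead of .035.
- Split between the two comparators (n = 150 each): .080 instead of .098.
- All to one comparator (n = 200): .069 instead of .098.

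**The case against.** **The bounds are upper limits and they hold.** This is correct. Every row of the table lies below .24 and .13, and so does every allocation of the extra 100. A reader might infer that the bounds are arithmetically wrong for these sizes; the documents do not support that. What remains is that they are loose and their basis is not stated.

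**The group sizes are approximate, and section 5.0 gives a range.** The approximation signs could absorb small rounding, but hardly 100 patients when the comparators are about 100 each. The range of 800 to 1100 concerns total recruitment. The sample-size statement commits to 1100 and itemises that figure, so the range does not explain the gap.

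**Censoring or a simultaneous band could widen the intervals.** This is fair, and it is why no single multiple of the stated bounds to the expected half-widths is reliable. With an assumed band critical value near 3, the 6-to-60-month pattern at month 48 gives about .138 × 3/1.96 = .21 for n = 100, not far from .24. For n = 800 the same step gives about .049 × 3/1.96 = .075, still well below .13. No variant tried gives both figures.

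**The ratio of the two bounds.** A reader might note that (.24/.13)² = 3.4 while 800/100 = 8, and conclude that the bounds belong to other group sizes. That needs the same recurrence and censoring in every group. Section 1.0 says that recurrence is higher after dilation and appears lower after open surgery. Separately chosen ceilings also need not scale with 1/√n. Nor do the documents show that the figures were carried over from a smaller design.

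**The consequence is limited.** This is an observational cohort with no power claim, and no analysis changes. That bears on how serious the point is, not on whether the statement should be corrected.

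**Conclusion.** The mismatch in the total is certain and rests on no assumption: the breakdown of 1100 accounts for 1000, and nothing in the documents places the other 100.

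The bounds are satisfied but uninformative. Across the follow-up patterns tried up to month 48 and the uncensored Hall-Wellner band, half-widths run from .098 to .138 for n = 100 and from .035 to .049 for n = 800, against stated limits of .24 and .13. The censored values assume exponential recurrence, the two uniform follow-up patterns and the worst-case survival probability; later time points or heavier censoring would widen them. The bounds cannot be reproduced because the statement gives no time point, follow-up, censoring or interval type.

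A reader might also infer that the study is too small. The documents do not support this: on these calculations, the sizes listed give tighter intervals than the plan claims. The sample-size statement should be corrected, but the design is not in question.

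**What to change.** In section 12.0, Sample Size Considerations:

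1. Make the total and the group sizes agree. Either restate the total as about 1000, or say which group holds the other 100. Keep the result consistent with the range in section 5.0, and use one name for the dilation group.
2. Replace .24 and .13 with half-widths recomputed for the reconciled sizes at a named time point. State the interval or band type, chosen from those listed in the Final Analysis Plan, and the follow-up and censoring assumed.

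The uncensored values .098 and .035 should not be inserted as ceilings, since censoring widens them. The choice between pointwise intervals and simultaneous bands is for the authors to make and state.

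The cost is a wording change and a short recalculation. No change in enrolment is needed.
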